- Enrolment – with the exclusion of patients with indeterminate or not classified colitis and that have participated in interventional clinical trials during the last 3 years. In fact, during a trial the subject has access to special and specific treatment and diagnosis procedures. The participation in an interventional trial during the previous 3 years may cause misunderstanding about treatment patterns and resources utilization, because in this project the retrospective data will be collected exactly about this period.
- Statistical analysis – with the inclusion in the logistic regression models of variables associated with both disease control and other variables of interest.

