## **6 DETERMINATION OF SAMPLE SIZE**

However, it is expected to include approximately 400 patients regardless of IBD type. This sample size will allow estimates with 95% confidence interval and a margin of error less than 5%. Based on the above and considering an expected ratio of CD/UC of approximately 50%50%, and that the rate of inadequate control of disease activity varies from 20-30% (regardless of the IBD type), it is expected to analyze 40-60 patients with CD and 30-50 patients with UC during the 12-month follow up.

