## **7 STATISTICAL ANALYSIS**

### **7.1 General considerations**

As the study is an observational study, epidemiologic methods will be performed in the data analysis. A descriptive analysis will be obtained for all relevant variables, with absolute and relative frequency for categorical variables and mean, standard variation, median, maximum and minimum (or range) for continuous ones. For each study endpoint, data will be summarized by IBD type (CD or UC). The variable normality assumption will be tested using the Kolmogorov-Smirnov test. Non-parametric tests will be used whenever the assumptions for parametric tests are not accepted. Statistical tests will be performed considering bilateral tests and a significance level of 0.05.

All statistical analyses will be performed using the statistical software SAS® (version 9.4; SAS Institute Inc., Cary, USA).

The statistical analysis of the study include a cross-sectional analysis (at the end of the cross-sectional study) and a longitudinal analysis (at the end of the 12-month follow-up period). No interim analyses are planned.

- Cross-sectional analysis: it is expected to obtain a characterization of the study population, the estimation of primary endpoints and the comparison of the subgroups of patients with no or mild activity of disease and those with moderate to severe activity. Hence, for each IBD type, the patients with disease activity will be compared with patients with no or mild activity regarding socio-demographic, clinical and treatment variables of interest. Further details of this analysis are described in Section 7.5 and 7.6.
- Longitudinal analysis will be calculated the proportion of controlled patients after 12-month follow up assessment, as well if applicable, logistic regression will be used for calculating odd ratios and 95% confidence intervals for the patient control at month 12 determined by independent variables. Further details of this analysis are described in Sections 7.5 and 7.6.

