## 7.6 Secondary Analysis

The secondary analysis include both a cross-sectional analysis and a longitudinal analysis.

The cross-sectional will be performed for cross-sectional analysis dataset:

- A descriptive statistical analysis will be performed for socio-demographic, anthropometric and clinical aspects of IBD by type (CD and UC);
- A descriptive statistical analysis will be performed for the treatment patterns for CD and UC in the previous 3 years, including the use of biologic therapies and failure to these therapies (if any), time between IBD diagnosis and initial treatment, first treatment after diagnosis of moderate to severe IBD, among other variables of interest.
- For each type of IBD (CD or UC), a comparison of patients with moderate to severe activity and patients with no or mild activity disease regarding socio-demographic, clinical and treatment variables of interest will be performed:
  - For qualitative variables, such as gender, smoking habits, professional status, family history of IBD, steroid behavior (dependent/refractory), previous treatment with biologic therapies, and previous surgery for IBD, the assessment of a significant difference between groups will be done using the Chi-Square Test or the Fisher's Exact Test depending if the assumption of cell frequency to be made;
  - For quantitative variables, such as age, time since diagnosis, and duration of treatment, such as age, time since diagnosis, and duration of treatment, the assessment of a significant difference between groups will be made through the t-test

- for independent samples or Mann-Whitney test in case of non-normality of the quantitative variable distribution;
- If applicable, for CD and UC patients, the assessment of independent variables which can be associated with disease control at day 1 will be performed using a logistic regression model. The odds ratios (ORs) estimates and the respective 95% confidence intervals will be presented.
- For each IBD (CD and UC), a descriptive statistical analysis (global and according to disease activity) for the quality of life data will be performed:
  - EuroQoL questionnaire (EQ-5D-5L) considers five attributes of quality of life evaluation:
    - Mobility;
    - Self-care;
    - Usual activity;
    - Pain/discomfort;
    - Anxiety/depression.
- Each dimension has five possible levels, 1-no problems, 2 slight problems, 3-moderate problems, 4-severe problems, 5-extreme problems.
- The resulting score of EQ-5D analog scale:

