  - For quantitative variables, the assessment of a significant difference between groups will be made through the t-test for independent samples or Mann-Whitney test in case of non-normality of the quantitative variable distribution;
  - If applicable, for patients with CD and UC, the assessment of independent variables which can be associated with the disease control (no or mild activity) after 12 months

follow-up will be performed using a logistic regression model. The ORs estimates and the respective 95% confidence intervals will be presented.

- If applicable, a survival analysis, with Kaplan Meier curves and Cox regression models to identify factors associated with the time of achieving mild or no activity with baseline treatment (continued or initiated at baseline) (dependent variable) will be performed for each type of IBD. The event of interest will be: have mild activity or no active disease. Thus, patients who remained with active disease or who change treatment due to lack of disease control will be censored and, conversely, success will be defined as having mild or no active disease. The survival analysis will include:
  - A non-parametric estimation of the survival function using the Kaplan-Meier estimator (global and stratified by categories for each categorical variable).
  - A comparison of estimated survival function curves of the different categories in each variable using the Log-Rank non-parametric test.
  - If applicable, the semi-parametric Cox proportional hazards model will be adjusted to identify potential factors associated with the time of achieving mild or no activity with baseline treatment (continued or initiated at baseline). The hazard ratios (HR) estimates and the respective 95% confidence intervals will be presented.
- A descriptive statistical analysis will be performed for the number and reason for treatment changes, as well for treatment patterns during the 12 month follow-up period by IBD type (CD and UC);
- For each type of IBD (CD or UC), a comparison of patients with treatment changes with those without changes 12 month follow-up, regarding main socio-demographic, clinical and treatment-related variables (at baseline) will be performed
  - For qualitative variables, the assessment of a significant difference between groups will be done using the Chi-Square Test or the Fisher's Exact Test depending if the assumption of cell frequency to be made;

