## 8 PROTOCOL CLARIFICATIONS/AMENDMENTS

As the amendments will not affect the data collection plan, this SAP was written in accordance with the information contained in Amendment 1 of study protocol, Version 17 Oct 2016. Since the Amendment was implemented at the end of the recruitment period at only one center and after the recruitment for the remaining centers, the section “Disposition of Subjects” will specify how many subjects were included based on the eligibility criteria described in the Amendment.

The following statistical analysis not described in the protocol should be considered:

- 1) General considerations: for each study endpoint, data will be summarized by study sites. Study sites can be classified as region: PI, BA, MG, GO, SP, PR, RS and RJ (Figure 2). The study sites/region should be considered as independent variable to be included in the regression models for the comparison of patients with no or mild activity with patients with disease activity.

[figure not shown]

Figure 2 – Study sites by region.

- 2) Subject's disposition: The study deposition should also be presented by IBD type and regions.
- 3) Demographic and other characteristics: The descriptive statistical analysis should also be performed by regions.
- 4) Primary Analysis: The proportion of patients with moderate to severe CD or UC should be calculated and compared by regions.
- 5) Secondary Analysis: For cross-sectional analysis dataset the descriptive statistical analysis will be performed also by region. The multivariate logistic regression model should include as independent variables all variables with  $p < 0.020$  in bivariate analysis. Optimized model present only variables with statistical significant OR (Odds Ratio). The region should be included as independent variable. For longitudinal analysis dataset the proportion of patients with moderate to severe CD or UC after 12 month follow-up should be calculated and compared by region. As for cross-sectional analysis dataset, the multivariate logistic

regression model should include as independent variables all variables with  $p < 0.020$  in bivariate analysis. Optimized model present only variables with statistical significant OR (Odds Ratio). The region should be included as independent variable.

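### Keeping only significant odds ratios (region apart) in the SAP's final logistic models can drop confounders that protocol 6.2 says will be included, and tends to exaggerate the odds ratios presented

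*SAP*

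**What the plan says.** SAP section 8 item 5 describes the multivariable logistic models. Variables enter if they pass a bivariate screen at p < 0.020. Then: "Optimized model present only variables with statistical significant OR (Odds Ratio". The sentence appears twice, once for the cross-sectional (Day 1) models and once for the longitudinal (12-month) models. One variable is protected: "The region should be included as independent variable". The note that closes the item list in section 8 repeats this. SAP 7.1 sets the threshold: "Statistical tests will be performed considering bilateral tests and a significance level of 0.05".

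SAP 7.6 says how the models are reported. For Day 1: "The odds ratios (ORs) estimates and the respective 95% confidence intervals will be presented". For month 12: "The ORs estimates and the respective 95% confidence intervals will be presented". Neither place mentions that the model was selected. The index of tables lists one logistic table per disease and time point: Tables 49 and 50 for Day 1, Tables 99 and 100 for month 12.

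Protocol 6.2 states how confounding will be handled at the analysis stage: "with the inclusion in the logistic regression models of variables associated with both disease control and other variables of interest".

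**The concern.** The two documents use different rules for what stays in the model. The protocol admits a variable because it is related to disease control and to the other factors under study. The SAP keeps it in the final model only if its own odds ratio is significant. Whether a variable confounds depends on its links with exposure and outcome, not on whether its own test reaches 0.05 in a sample of this size. A variable can therefore be exactly what protocol 6.2 has in mind and still be removed.

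There is a second, separate effect. If an odds ratio is shown only when it is significant, the ones shown are a selected group that tends to lie too far from 1. An ordinary 95% interval around a selected estimate need not cover the true value 95% of the time.

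At stake are the models of factors associated with disease control at Day 1 and at month 12. Protocol 6.2 gives insight into such factors at month 12 as a reason for the prospective phase.

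**Working it through.** **Model sizes.** The documents give no bias or coverage figure for these models. The figure that sizes them is the total: "it is expected to include approximately 400 patients regardless of IBD type", with a stated margin of error below 5%. That reproduces for the pooled sample: 1.96 × √(p(1−p)/400) is 3.9% at p = 0.20, 4.5% at 0.30 and 4.9% at 0.50. The models are per disease, so a 50/50 split gives 400 × 0.5 = 200 patients each at Day 1. Protocol 10.6 and SAP 6 expect 40–60 Crohn's disease and 30–50 ulcerative colitis patients at 12 months. Region has eight levels ("Study sites can be classified as region: PI, BA, MG, GO, SP, PR, RS and RJ"), which uses 8 − 1 = 7 parameters.

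**Assumed inputs, not in the documents.** One binary exposure with true adjusted odds ratio 1.5. One binary confounder with odds ratio 1.8 and prevalence 40%. Exposure present in 60% of patients with the confounder and 30% of those without. Baseline risk 20% at n = 200 and 50% at n = 50. Model: logit P(Y=1) = b₀ + ln(1.5)·exposure + ln(1.8)·confounder. Backward elimination at p ≥ 0.05 is my reading of how the final model is reached. There were 4,000 data sets per scenario. The entry screen and region were left out, to isolate the retention rule.

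**Results: median exposure odds ratio and 95% CI coverage (true value 1.5).**

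| Reporting rule | n = 200 | n = 50 |
|---|---|---|
| Full model, always reported | 1.5, 95% | – |
| Full model, reported only if exposure is significant | 2.27, 88% | 5.19, 72% |
| After elimination, reported only if exposure is significant | 2.31, 82% | 4.8, 71% |

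The confounder is dropped in about 50% of data sets at n = 200 and 83% at n = 50. At n = 200 the exposure is presented in about 29% of data sets, roughly 1,160 of 4,000. The simulation error on 82% coverage is therefore about √(0.82 × 0.18/1,160) = 1.1 percentage points.

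**Separating the two effects.** The second row is the comparison that matters, because rows two and three share the same condition. At n = 200 the filter alone multiplies the odds ratio by 2.27/1.5 = 1.51; filter and elimination together give 2.31/1.5 = 1.54. Nearly all the exaggeration is the filter. For coverage the shares are closer: 95 − 88 = 7 points from the filter and 88 − 82 = 6 from elimination. At n = 50 the filter accounts for essentially everything. Omitting the confounder with no filter moves the median odds ratio only from 1.5 to about 1.77.

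**Sensitivity at n = 200.** With the same confounder, a true odds ratio of 2.0 gives 2.55 and 92%; 3.0 gives 3.30 and 95%. A confounder with odds ratio 3 is dropped in only 5–8% of data sets. With negative confounding (true 2.0), coverage is 96%.

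**A setup closer to the SAP.** This one forces region in, applies the p < 0.020 screen, adds ten null candidates, and uses a normally distributed confounder with odds ratio 1.4 per SD correlated with the exposure (latent correlation 0.5). At n = 200:

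| True odds ratio | 40 events | 60 events |
|---|---|---|
| 1.5 | 3.08, 64% | 2.62, 71% |
| 2.0 | 3.29, 85% | 2.88, 87% |
| 3.0 | 4.15, 91% | 3.69, 91% |

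A prespecified model with exposure, confounder and region, always reported, gives 1.50–1.56, 2.05–2.11 and 3.20–3.27, with coverage 93–96%. Relaxing the screen to 0.20 (40 events, true 2.0) changes the result from 3.29 to 3.22, with coverage 85% either way, so the retention rule matters whatever the entry threshold. At a 25% active rate and true 2.0, the split is 3.31 and 76% when the confounder is lost, 2.69 and 96% when it is kept. With no confounding at all the rule still gives 2.81 and 91%.

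**The case against.** Several points on the other side stand.

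- A reader might infer that the exaggerated odds ratios arise because the retained factor absorbs the effect of a dropped confounder. The like-for-like comparison does not support that: the filter produces nearly all of the exaggeration in the first setup.
- A reader might infer that the rule removes every non-significant variable. Region is explicitly kept, and strong confounders mostly pass their own test.
- A reader might infer that only the reduced model will be shown. Item 5 can also be read as two models, one with all screened variables and then the optimized one. The shells for Tables 49, 50, 99 and 100 are not in the text available, so this cannot be settled. What can be said is that no available text commits to showing the fuller model.
- Protocol 6.2 names no confounders, no main exposure and no threshold, so it is a principle rather than a worked specification. The conflict is over the principle.
- The models are to be run only if applicable, and no listed secondary objective is worded as identifying factors associated with control. The listed comparisons rest on the bivariate tests (Tables 42–48 and 91–98), which are not filtered.
- The sizes depend on assumed inputs. A true odds ratio of 1.5 is an unfavourable case.

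None of this answers the central point. The SAP states a significance-only rule twice, protects nothing but region, and reports ordinary intervals afterwards.

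**Conclusion.** The point holds in a limited form. The SAP's retention rule conflicts with the confounding principle in protocol 6.2 and can remove weak or moderate confounders. It also selects odds ratios by significance, so presented values tend to be too far from 1. Under-coverage is possible rather than certain: clear with positive confounding and modest true effects, slight when true effects are large, and absent with moderate negative confounding.

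For one disease at Day 1, with true odds ratio 1.5 and confounder odds ratio 1.8, expect a presented median of about 2.3 with 82% coverage. The 12-month models are worse, mainly because they are small. These figures rest on assumed effects, prevalences and an elimination procedure that the documents do not specify.

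A reader might go on to infer that the study's main findings are compromised. They are not: the primary proportions of patients with active disease do not pass through these models. This is worth correcting, but it is a matter for the secondary regressions only.

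**What to change.** Replace the optimized-model sentence in both places in SAP section 8 item 5 with wording to this effect: the multivariable model before elimination is the main result in Tables 49, 50, 99 and 100; every odds ratio and 95% interval in it is shown, significant or not; and a short list of confounders named before analysis, together with region, is kept whatever the p-values. A reduced model may be shown beside it as secondary, with a note that its intervals ignore the selection.

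The cost is a change of wording, agreement on the confounder list, and one more column in four tables. No new data are needed. Intervals will be wider and fewer factors will be significant.

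The change does not cure sparseness at 12 months. With 30–60 patients per disease and 7 parameters taken by region, even a prespecified model ran high in the simulation (true 2.0, median 2.27–2.53 at 40–60 patients). The 12-month confounder list must therefore be very short and the estimates labelled exploratory.

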## **9 DISCREPANCY IN RETROSPECTIVE DATA AFTER DATABASE LOCK**

Any discrepancy in retrospective IBD medication data found after the database lock will be corrected in case of: primary analysis is affected, there is more than 5% of error on data used for secondary analysis. The impact on published information should also to be weighted. The percentage of discrepancies at study medication will be evaluated and a re-analysis will be performed only if previous criteria apply. The new analysis will be included in the final report which includes the updated (new version) retrospective analysis and prospective analysis and results.

